**BOTE Inflammation Score**

Score	Global Assessment	Description
0	No inflammation	No evidence of local inflammation
1	Mild	Minimal erythema and/or edema
2	Moderate	Definite erythema and/or edema with or without hemorrhagic crusting
3	Severe	Erythema and edema with definite hemorrhagic crusting
4	Very severe	Strong reaction spreading beyond the treated area, bullous reaction, erosions

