## 12. OTHER ANALYSES

The following analyses of BOTE vs lesion count will be presented:

- Percent change from Baseline in the number of treatable MC at each visit in relation to the Baseline BOTE score comparing No Inflammation vs Inflammation within each treatment group through a repeated measures mixed model with number of randomly assigned subjects in household (1 subject vs 2 subjects), investigator type (dermatologist

vs other), BOTE score at Baseline (no inflammation [BOTE=0] vs mild/moderate/severe/very severe inflammation [BOTE $\geq$ 1]), BOTE score at Baseline by visit interaction, age, and baseline lesion count as covariates with a compound symmetry covariance matrix.

- Percent change from Baseline in the number of treatable MC at Week 12 in relation to the highest post-baseline BOTE score during treatment will be summarized descriptively.
- Percent change from Baseline in the number of treatable MC at Week 12 in relation to the highest BOTE score at any visit (including Baseline) will be summarized descriptively.
- Percent change from Baseline in the number of treatable MC at each visit in relation to the BOTE score at Week 2 will be summarized descriptively.

In these analyses, the BOTE scores will be analyzed in the ITT Population as follows:

1. Dichotomized:
  - a. Score of 0: No Inflammation
  - b. Score of 1, 2, 3, or 4: Mild to Very Severe

A shift table comparing the baseline BOTE score to each scheduled post-baseline assessment will be presented for the ITT Population.

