### **13.3 Events of Special Interest**

Events of Special Interest will include subjects with any TEAE where the preferred term contains “application site”, subjects with at least 1 post-baseline occurrence of moderate BOTE inflammation score, or subjects with at least 1 post-baseline LSR component score  $\geq 1$ . A summary including the number and percentage of subjects with at least 1 event of special interest, AEs of interest by MedDRA system organ class and preferred term, at least 1 moderate BOTE inflammation score, and any LSR component score  $\geq 1$  will be provided for the Safety Population. The analysis will also be repeated with the LSR criteria revised to include any post-baseline LSR component (excluding erythema) score  $\geq 1$  and erythema score  $\geq 2$ .

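### The BOTE part of the event-of-special-interest definition (SAP 13.3) counts score 2 only, so its summary row can omit subjects who score 3 or 4

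*SAP*

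**What the plan says.** SAP section 13.3 counts a subject as having an event of special interest if any one of three criteria is met:

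- an application-site event: "subjects with any TEAE where the preferred term contains" the words application site;
- inflammation on the BOTE scale: "subjects with at least 1 post-baseline occurrence of moderate BOTE inflammation score";
- a local skin reaction: "subjects with at least 1 post-baseline LSR component score" of 1 or more.

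The summary, planned for the Safety Population, gives each criterion its own entry. The BOTE entry is "at least 1 moderate BOTE inflammation score". Appendix C lists the output as Table 14.3.6.2.

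The BOTE scale is set out in SAP section 4 and, identically, in protocol section 7.1.2.1. Its three upper grades are:

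- 2, moderate: "Definite erythema and/or edema with or without hemorrhagic crusting"
- 3, severe: redness and swelling must both be present, and the crusting is no longer optional
- 4, very severe: "Strong reaction spreading beyond the treated area, bullous reaction, erosions"

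**The concern.** Moderate is the name of one grade on this scale. It does not by itself mean that grade and everything above it. As written, the rule counts a subject with a score of 2 but not a subject who goes straight to 3 or 4.

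A count of notable reactions should not go down when a reaction becomes worse, and this one can. A reader of Table 14.3.6.2 would naturally take the BOTE row as the number of subjects with at least moderate inflammation. If the row is programmed to the letter, that reading would be wrong, and wrong at the severe end of the scale.

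**Working it through.** The plan states no figure for this point, so the check compares the definition with the scale.

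**1. Which scores meet the BOTE criterion?**

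| BOTE score | Grade | As written (score = 2) | Moderate or worse (score ≥ 2) |
|---|---|---|---|
| 0 | None | no | no |
| 1 | Mild | no | no |
| 2 | Moderate | yes | yes |
| 3 | Severe | **no** | yes |
| 4 | Very severe | **no** | yes |

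The two readings differ for a subject whose highest post-baseline score is 3 or 4 and who has no recorded 2.

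**2. Can that happen on this visit schedule?** Post-baseline BOTE scores are scheduled at Weeks 2, 4, 8 and 12 (protocol Table 1). Take two hypothetical subjects:

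- Scores 1, 2, 1, 0: counted.
- Scores 1, 3, 1, 0: not counted.

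The second subject had the worse reaction. With two to four weeks between assessments, a score can pass through 2 without being recorded there.

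The possible patterns can be counted. Four visits with five grades give 5⁴ = 625 patterns.

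- Patterns reaching at least 2: 625 − 2⁴ = 609.
- Patterns containing a 2: 625 − 4⁴ = 369.
- Patterns reaching 3 or 4 with no 2: 609 − 369 = 240.

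These are logical possibilities and not rates. They show only that the two readings are not equivalent.

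**3. Does the SAP use a single grade name to mean a range elsewhere?** It does not. Where it means several BOTE grades it lists them or gives a threshold. Section 12 has "Score of 1, 2, 3, or 4: Mild to Very Severe", and sections 4, 9.3, 10.3 and 10.6 define the inflamed category as BOTE of 1 or more with every grade named. In the very sentence at issue, the LSR criterion carries a threshold and the BOTE criterion does not.

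**4. Do the other two criteria pick these subjects up?** They may, but no rule ensures it.

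- *LSR.* The LSR scale rates erythema, swelling, crusting, vesiculation and erosion, which overlap with the signs that define BOTE 3 and 4. A single component score of 1 is enough. Both scales are completed at every scheduled visit through Week 12 (protocol section 6.6). However, SAP section 4 asks investigators to judge BOTE and LSR separately, so a high BOTE score does not by rule produce an LSR score.
- *Adverse event.* SAP section 4 says BOTE is not to be treated as an adverse event, so a high score alone does not enter by this route.

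Neither route puts the subject in the BOTE row itself.

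**5. Are scores 3 and 4 reported elsewhere?** They are, by visit and by subject:

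- SAP section 12 plans a shift table of BOTE score from baseline to each visit in the ITT Population.
- Appendix C lists Table 14.2.3.12.5, BOTE results by visit, also ITT. No separate shift table is titled there, so this may be the same output.
- Listing 16.2.9.1 gives individual scores.

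None of these is a per-arm count of subjects who ever reached moderate or worse. The section 12 summaries by highest BOTE score are dichotomised as 0 against 1 to 4, so they do not supply that count either.

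**The case against.** The strongest reply is that little is lost. The event of special interest is a composite joined by *or*, and its LSR criterion is very low: slight pinkness or isolated crusting suffices. A subject with a BOTE score of 3 or 4 would plausibly qualify that way, so the overall count may hardly move. Scores 3 and 4 are visible in other outputs. Protocol section 10.3.4 plans no inferential statistics for safety endpoints, and the documents tie no monitoring or stopping decision to this row. *Moderate* may be shorthand for moderate or worse, and the table shells, held in a separate file not available here, may say so.

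Most of that stands, and it sets the size of the point. It does not remove the point: the row has its own definition, and the SAP text gives only one grade for it.

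Three stronger readings are tempting, and the documents do not support them.

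- *Severe inflammation cannot be an event of special interest.* It can, through the LSR or application-site criterion, or through a score of 2 at another visit.
- *The worst cases vanish from the report.* They do not; see the shift table, Table 14.2.3.12.5 and Listing 16.2.9.1.
- *The omission favours the active arm, because severe scores are likelier there.* The documents contain no BOTE frequencies by arm. In the earlier phase 3 trials (protocol Tables 3 and 4), moderate application-site erythema was reported in 15 of 235 SB206 against 1 of 116 vehicle subjects, and in 14 of 237 against 0 of 117. Severe application-site erythema occurred in 1 of 235 and 2 of 237 SB206 subjects and in no vehicle subjects. These are adverse events and not BOTE scores, and the plan describes BOTE as a sign of natural resolution. They establish neither a direction nor a size for BOTE.

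**Conclusion.** The BOTE criterion and its summary row in SAP 13.3 are wrong as written, with minor severity. Taken literally, they are met by score 2 alone, and the row can decrease as severity increases. The defect lies in one criterion and one row of a descriptive safety table; the primary and secondary efficacy analyses are untouched.

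The number of subjects affected, and any imbalance between arms, cannot be computed from the documents. The effect on the overall event-of-special-interest count is probably smaller than on the BOTE row, if LSR scores track high BOTE scores as the overlap of signs suggests; that is an expectation and not a stated fact.

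The conclusion rests on one assumption: that the table is programmed from the SAP wording. If the shells already specify scores 2 to 4, the remaining problem is that the SAP text disagrees with them.

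**What to change.** In SAP section 13.3, replace *moderate* with *moderate or worse (BOTE score ≥2)* in both the definition and the description of the summary. Make the shell for Table 14.3.6.2 match. Do this before the Week 12 database is frozen and unblinded (SAP section 6), so that the definition is fixed without knowledge of treatment.

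The cost is a wording change in one section and one shell. The BOTE scores are already collected at every visit concerned, so no new data, visit or procedure is needed.

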7.2 Safety Assessments

7.2.1 Physical Exam

A brief physical examination will be performed to evaluate objective anatomic findings. This physical examination will be performed at Baseline and at Week 12/ET. At Baseline, the physical examination will include a directed examination of the skin condition prior to any

application of study drug. This skin assessment will include the presence or absence of individual features of erythema, flaking/scaling, crusting, swelling, vesiculation/pustulation, and erosion/ulceration. Any clinically significant changes in the physical exam from baseline will be recorded as AEs.

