Prior to the first application of study drug at Baseline, the investigator will assess the subject's skin as part of the physical examination, including the presence or absence of individual features of erythema, flaking/scaling, crusting, swelling, vesiculation/pustulation, and erosion/ulceration. At Baseline (at least 30 minutes after dosing) and Week 2 through Week 12, the investigators will rate LSRs on individual features including erythema, flaking/scaling, crusting, swelling, vesiculation/pustulation, and erosion/ulceration using the LSR Assessment Scale.

The following tables describe the scoring parameters for the BOTE Inflammation Score and LSR score.

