**LSR Score**

Score	Erythema	Flaking/Scaling	Crusting	Swelling	Vesiculation/Pustulation	Erosion/Ulceration
0	Not present	Not present	Not present	Not present	Not present	Not present
1	Slightly pink	Mild, limited	Isolated crusting	Minimal, limited	Fine vesicles	Superficial erosion
2	Pink or light red	Moderate	Crusting < 50%	Mild, palpable	Scant transudate or exudate	Moderate erosion
3	Red, restricted to treatment area	Coarse	Crusting > 50%	Moderate	Moderate transudate or exudate	Marked, extensive
4	Red extending outside treatment area	Scaling extending outside treatment area	Crusting extending outside treatment area	Marked swelling extending outside treatment area	Marked transudate or exudate	Black eschar or ulceration

Adverse events will be assessed and collected after the initiation of study drug treatment through the end of the subject’s last visit. Treatment-related AEs and all serious adverse events will be followed up until resolution or up to one year after last treatment, whichever is sooner.

Scar formation (scars/keloids/hypertrophic scars) will be assessed starting at the Week 4 visit through Week 24. The investigator will map locations of the molluscum lesions at Baseline. Additional lesions identified through Week 12 will be added to the map. Using the map as a guidance, the investigator will assess the treated areas for scar/keloid formation. All scars, including keloid/hypertrophic scars, that develop after the Baseline assessment should be captured as AEs and assessed for relatedness to study treatment.

If a subject's treatment is discontinued by the investigator or the subject because of an AE, that AE should be indicated as the reason for treatment discontinuation. All subjects will be encouraged to remain in the study and to complete all required study visits throughout the 24-week study duration.

When approximately 200 subjects are randomized, a data safety monitoring board (DSMB) will review all available unblinded safety data (including completed patch testing results). The DSMB will provide their recommendation for the study to proceed or not proceed.

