#### 13.1 Adverse Events

Adverse event summaries restricted to treatment-emergent AEs (TEAEs) will include those AEs that occurred any time on or after the first in-clinical application of study drug through the last application of study drug and those existing AEs that worsened during this same period. If it cannot be determined whether the AE is treatment emergent due to a partial onset date, then it will be counted as such; see Appendix A for the imputation of missing dates algorithm. Post treatment AEs will include those AEs that occurred after the last application of study drug. Verbatim terms in the eCRFs will be mapped to preferred terms and system organ classes using the MedDRA Version 23.0 or later.

Each AE summary will be displayed by treatment group. Summaries that are displayed by system organ classes and preferred terms will be ordered by descending order of incidence in SB206 treatment group of system organ class and preferred term within each system organ class. Summaries of the following types will be presented:

- Overall summary of TEAEs and post treatment AEs that contain an overview of each item below.

- Subject incidence of TEAEs with total number of unique TEAEs and post treatment AEs with total number of unique post treatment AEs by MedDRA system organ class and preferred term.
- Subject incidence of TEAEs and post treatment AEs by MedDRA system organ class, preferred term, and maximum severity. At each level of subject summarization, a subject is classified according to the maximum severity if the subject reported 1 or more events. Adverse events with missing severity will be considered severe for this summary.
- Subject incidence of TEAEs by MedDRA system organ class, preferred term, and closest relationship to study drug (Related/Not Related). Related AEs are those reported as “Definite,” “Probable,” or “Possible,” and unrelated AEs are those reported as “Unlikely” or “Unrelated.” At each level of subject summarization, a subject is classified according to the closest relationship if the subject reported 1 or more events. Adverse events with a missing relationship will be considered related for this summary.
- Subject incidence of serious TEAEs with total number of unique serious TEAEs and post treatment serious AEs with total number of unique post treatment serious AEs by MedDRA system organ class and preferred term.

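### The LSR and BOTE limbs of the event-of-special-interest rule do not require worsening from the pre-dose state, so persisting pre-treatment signs count as events and dilute the descriptive arm difference.

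*SAP*

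**What the plan says.** SAP 13.3 defines an event of special interest by three alternative limbs:

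- a TEAE whose preferred term contains the application-site wording;
- "subjects with at least 1 post-baseline occurrence of moderate BOTE inflammation score";
- "or subjects with at least 1 post-baseline LSR component score" of 1 or more.

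The summary gives the overall proportion and each limb separately. A second version follows: "The analysis will also be repeated with the LSR criteria revised to include any post-baseline LSR component (excluding erythema) score" of 1 or more, with erythema counted from 2.

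The AE limb inherits the TEAE definition in SAP 13.1, which admits new events and "those existing AEs that worsened during this same period".

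Three kinds of baseline information exist:

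- BOTE is scored 0 to 4 before dosing (Protocol, Table 1 footnotes and Section 6.6).
- The LSR scale is first used after dosing: "At Baseline (at least 30 minutes after dosing) and Week 2 through Week 12, the investigators will rate LSRs on individual features" (SAP 4).
- The same six features are examined before the first dose, but not graded. Protocol 7.2.1 says: "This skin assessment will include the presence or absence of individual features".

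SAP 10.2 defines baseline as the last value before the first application. SAP 13.2 plans change from Baseline in the LSR composite, a shift table for each LSR parameter, and LSR summaries split by dichotomized baseline BOTE. SAP 12 plans a BOTE shift table.

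**The concern.** One composite mixes a treatment-emergent limb with two limbs that measure prevalence. The lowest LSR grade is slight; for erythema it is "Slightly pink". Subjects with inflammation at entry are admitted, and baseline BOTE of 1 or more is a stratification level. The BOTE grades are described by erythema, edema and crusting, which overlap the LSR components erythema, swelling and crusting.

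A subject who enters with a qualifying sign and stays the same is therefore reported as having had an event. Such subjects occur in both arms, raise both proportions and pull the arms together. The table describes local reactions, which led to every SB206-arm drug discontinuation in the two completed phase 3 trials (Protocol 2.1.4.2), so its contrast should reflect treatment as closely as the data allow.

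**Working it through.** **Step 1. Apply the rule as written.** The BOTE column takes the literal reading, in which moderate means a score of 2.

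| Pre-dose | Post-baseline | Current rule | With a worsening condition |
|---|---|---|---|
| BOTE 0 | BOTE 2 | event | event |
| BOTE 2 | BOTE 2 | event | no event |
| BOTE 3 | BOTE 2 | event | no event |
| LSR feature absent | score 1 | event | event |
| LSR feature present | score 1 | event | no event |

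The third line shows that even an improvement from severe to moderate is an event. In the repeat, an erythema score of 1 drops out, but the other five components still count from 1 and nothing is compared with the pre-dose state.

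**Step 2. Do other tables supply the missing comparison?** For BOTE they do, because its shift table starts from a scored pre-dose value. For LSR they do so only in part. The change and shift analyses start from a score taken after the first dose, which does not fit the SAP 10.2 definition of baseline and cannot show change from untreated skin. The pre-dose features feed no described table one by one; SAP 13.5 reduces the physical examination to a normal/abnormal shift.

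**Step 3. Size.** The documents give no event-of-special-interest rate, so there is no figure to reproduce. Let p be the rate of new or worsened signs in an arm, and b the share with qualifying pre-dose signs that persist to a post-baseline visit, taken as equal in both arms.

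Observed rate = b + (1 - b) × p

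Observed difference = (1 - b) × (p for SB206 - p for vehicle)

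Inputs:
- b is not given; it is varied from 0 to 90%.
- p is not given. As an assumed stand-in, take treatment-related TEAEs pooled over NI-MC301 and NI-MC302 (Protocol Table 2): SB206 (86 + 86)/(235 + 237) = 172/472 = 36.4%; vehicle (19 + 8)/(116 + 117) = 27/233 = 11.6%. These are AE rates, not LSR score rates.
- 425 subjects per arm (SAP 5).

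Example at b = 30%: SB206 0.30 + 0.70 × 0.364 = 55.5%; vehicle 0.30 + 0.70 × 0.116 = 38.1%.

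| b | SB206 | Vehicle | Difference (points) | Ratio | 95% CI of difference |
|---|---|---|---|---|---|
| 0 | 36.4% | 11.6% | 24.9 | 3.14 | 19.4 to 30.3 |
| 10% | 42.8% | 20.4% | 22.4 | 2.09 | 16.3 to 28.4 |
| 30% | 55.5% | 38.1% | 17.4 | 1.46 | 10.8 to 24.0 |
| 50% | 68.2% | 55.8% | 12.4 | 1.22 | 6.0 to 18.9 |
| 70% | 80.9% | 73.5% | 7.5 | 1.10 | 1.8 to 13.1 |
| 90% | 93.6% | 91.2% | 2.5 | 1.03 | -1.1 to 6.0 |

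The intervals are difference ± 1.96 × √[A(1 - A)/425 + V(1 - V)/425], where A and V are the observed SB206 and vehicle rates. They only indicate precision; the plan does not test safety endpoints.

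With other assumed rates, p = 50% vs 20%, b = 40% gives 70% vs 52%: the difference falls from 30 to 18 points and the ratio from 2.5 to 1.35.

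**The case against.** A sensitive absolute threshold is a legitimate choice for a descriptive safety screen. The table is listed under other safety data, is not a protocol safety endpoint, carries no test and shows its limbs separately. The AE limb is already treatment-emergent, and application site pain, the most common treatment-related event, can enter there. The protocol's abbreviation list describes an LSR as a reaction after exposure to study drug, and investigators are told to separate BOTE from LSR by judgement, so natural inflammation should mostly not be scored as LSR. The split by baseline BOTE separates subjects inflamed at entry.

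Most of this stands, and it limits the point's weight. It does not remove the point: the separate BOTE and LSR rows have the same gap as the composite, and the LSR shift tables start after dosing.

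Three stronger readings are tempting and not supported:

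- *The rule hides the arm difference.* The model gives dilution by (1 - b). On the stand-in rates the interval still excludes zero at b = 70%; the contrast is nearly lost only if background signs are almost universal.
- *Baseline inflammation must be common, because it is a stratification factor.* No prevalence is given, and a sign linked to imminent resolution is worth stratifying on at any frequency. The stratum is also wider (1 or more) than the moderate score in the rule.
- *Six components at four visits give 24 chances of a chance event.* At an assumed 5% per component-visit, 1 - 0.95^24 = 71% would qualify if scores were independent. That concerns the low cut-off and repeated looks, not pre-dose signs, and a worsening condition would largely leave it in place.

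**Conclusion.** The point holds as a gap in the definition. The LSR and BOTE limbs lack the worsening condition that the TEAE limb has, so pre-treatment signs scored again after baseline become events, in the main analysis and in the repeat. The effect is dilution of a descriptive contrast by (1 - b), with b unknown.

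The sizes rest on assumed values of b, on AE rates standing in for sign rates, and on equal b in the two arms. Randomisation balances pre-dose signs on average; their persistence on treatment could still differ by arm. No test or protocol endpoint is affected. The change is worth making because it costs little and makes the composite consistent within itself.

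**What to change.** In SAP 13.3:

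1. **BOTE limb.** Keep the existing threshold and also require the post-baseline score to exceed the pre-dose Baseline score. State whether moderate means 2 only or 2 and above, since severe and very severe are not named.
2. **LSR limb.** Add a treatment-emergent row: a component scored 1 or more post-baseline whose feature was recorded absent at the pre-dose skin examination. Apply the same condition to the planned repeat, with its erythema cut-off of 2. State whether the Day 1 post-dose LSR score counts as baseline or post-baseline.
3. **Keep the current absolute-threshold rows alongside.**

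Do not handle features already present pre-dose through a higher cut such as 3 or more. The documents give no basis for one; it would miss a rise from 1 to 2 and still count an unchanged grade 3.

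The cost is SAP wording and a short derivation from data that the protocol already collects, provided that the eCRF holds the six pre-dose features separately. The downside is small. The pre-dose examination records only presence or absence and is not stated to be limited to treated areas. The new LSR row can therefore miss worsening of a feature already present, or a new reaction at a treated site when the feature was present elsewhere. That is why the absolute rows stay.
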